This amendment incorporates recommendation from the European Union clinical trial review.

Protocol amendment summary of changes table

Section # and Name	Description of Change	Brief Rationale
1.3.1 Schedule of Activities	Footnote added to blood eosinophils and neutrophils to specify that a complete hematology panel will be performed at Visit 4, Visit 12 and follow-up Visit F1	Clarification for the biomarker (blood eosinophils and neutrophils) collection visits is provided in order to address the request from the Health Agencies review.
4.3 Justification for Dose	Details added to the justification for dose	Requested during the Health Agencies review of the clinical trial application.
5.2 Exclusion Criteria	Deleted E08: Participants with COPD diagnosed within the 6 months prior to randomization Modified E26: Known allergy to doxycycline or related compounds.	During the Health Agencies' review of the clinical trial application, an inconsistency was identified in the duration of COPD diagnosis required for study inclusion. As per inclusion criterion I01, patients with a diagnosis of COPD for at least 1 year are eligible for inclusion, whereas exclusion criterion E08 excluded participants with COPD diagnosed within the 6 months prior to randomization. The study intends to include patients diagnosed with for at least 1 year, therefore E08 is now deleted. Per the Healthy Agencies' request, the criterion is being modified to also exclude patients with a history of systemic hypersensitivity to any excipients of the IMP.

Section # and Name	Description of Change	Brief Rationale
	Modified E34: Patients with cardiovascular diseases/conditions: for uncontrolled hypertension	Per the Health Agencies' request, the exclusion criterion related to uncontrolled hypertension has been modified in order to exclude patients with grade 3 hypertension (high cardiovascular risk).
6.5 Concomitant Therapy	Removed intra-articular steroids from permitted concomitant therapy	Resolve an inconsistency as relevant systemic exposure may occur with intra-articular steroids. Systemic steroids are not permitted during the screening or treatment phases.
8.1.1.1 COPD exacerbation	Added "Any course of systemic steroids/antibiotics started <7 days of finishing a previous course should be considered as treatment for a single exacerbation"	Further clarification has been provided as regards reporting of COPD exacerbations.

1 PROTOCOL SUMMARY

1.1 SYNOPSIS

Protocol title: A randomized, double-blind, placebo-controlled, parallel-group, Proof-of-Concept (PoC) study to assess the efficacy, safety and tolerability of SAR440340, in patients with moderate-to-severe chronic obstructive pulmonary disease (COPD)

Short title: Proof-of-Concept study to assess the efficacy, safety and tolerability of SAR440340 (anti-IL-33 mAb) in patients with moderate-to-severe chronic obstructive pulmonary disease (COPD)

Rationale:

Chronic obstructive pulmonary disease (COPD) is a highly prevalent disease worldwide, associated with significant economic burden, and for which available standard-of-care therapy shows insufficient treatment effect on symptoms, lung function, exacerbations and long term evolution of the disease. Interleukin-33 (IL-33) is a pro-inflammatory cytokine that initiates and amplifies innate and adaptive inflammatory cascades, in response to epithelial cell stress or damage due to exposure to airborne allergens, viruses, cigarette smoke, and air pollutants. The objective of the current study is to investigate the effects of 300 mg SAR440340 (a human monoclonal antibody that targets IL-33), administered SC once every 2 weeks as compared to placebo on reducing the incidence of exacerbations in patients with moderate-to-severe COPD.

Objectives and endpoints

Objectives	Endpoints
Primary	

To investigate effects of SAR440340 (anti-IL 33 mAb) compared with placebo, on the annualized rate of moderate-to-severe acute exacerbations of COPD (AECOPD) over up to 52 weeks of treatment.	
Annualized rate of moderate*-to-severe** AECOPD over the treatment period.*Moderate exacerbations are recorded by the Investigator and defined as AECOPD that require either systemic corticosteroids (such as intramuscular, intravenous or oral) and/or antibiotics.** Severe exacerbations are recorded by the Investigator and defined as AECOPD requiring hospitalization, emergency medical care visit or resulting in death.
Key secondary	

To investigate effects of SAR440340 compared with placebo, on improving respiratory function, as assessed by pre bronchodilator FEV1 over 24 weeks.	
Average change from baseline to Week 16-24*** in FEV1 (pre-bronchodilator) 
*** Model-based averages across Weeks 16, 20 and 24 will be compared between the treatment groups

Overall design:

Multinational, randomized, double-blind, placebo controlled, parallel group (2 groups), Proof of Concept (PoC) study that is designed to assess the efficacy, safety, and tolerability of SAR440340 in patients with moderate-to-severe COPD on an established Long-acting β 2 adrenergic agonist (LABA), Long-acting muscarinic antagonist (LAMA), and/or ICS background therapy (double or triple therapy). Patients will be treated with SAR440340 or placebo for a minimum of 24 weeks and up to a maximum of 52 weeks*, and a 20-week safety follow-up period.

** This study employs a variable treatment duration from 24 to 52 weeks to maximize data for the primary endpoint (annualized rate of exacerbation) in a time-efficient manner. Patients enrolled in the trial will remain in the treatment period for up to a maximum of 52 weeks or until the last patient randomized completes a minimum treatment period of 24 weeks. Of note, the accrual and drop-out rates will be closely monitored. If the accrual rates are significantly lower than planned and/or the drop-out rates are higher than expected, the minimum treatment duration may be extended to achieve the desired amount of total exposure. The maximum treatment duration of 52 weeks will not be changed.*

The study duration is outlined below:

- Screening period (10 days to 4 weeks)
- Randomized investigational medicinal product (IMP) treatment period (24 to 52 weeks)
- Post IMP safety follow-up treatment period (20 weeks).

At screening, patients must be on standard of care background therapy, for 3 months prior to Visit 2/Randomization and at a stable dose for at least 1 month prior to the Screening Visit 1, including either:

- Double therapy: LABA + LAMA or ICS + LABA or ICS + LAMA.

OR

- Triple therapy: ICS + LABA + LAMA.

Patients who satisfy the inclusion and exclusion criteria will be randomized (1:1) to:

- SAR440340 (300 mg) administered as 2 SC injections every 2 weeks (q2w) for 24 to 52 weeks
- Matching placebo for SAR440340 administered as 2 SC injections q2w for 24 to 52 weeks

It is planned to enroll approximately 50% of patients on ICS-containing background therapy (ICS+LABA; ICS+LAMA or ICS +LABA+LAMA).

Patients must be willing to stay on their established background medication for COPD throughout the duration of the study.

Visits up to 52-week IMP treatment period will occur every other week and will be followed by a 20-week observational follow-up period.

Treatment discontinuation follow-up:

Patients who withdraw from study treatment (prior to completing the planned duration of IMP treatment) will perform, as soon as possible, the early treatment discontinuation visit (ETD) with all assessments normally planned for the EOT visit, to assure a complete clinical assessment in close temporal proximity to the premature termination of study treatment is available. In addition, and to allow assessment of patient outcomes over the stipulated study period, patients will be asked and encouraged to complete all remaining study treatment visits, and participate in all safety follow-up assessments according to the visit schedule with a +/-5 day window. For such patients the assessment schedule will be reduced (See study flowchart for patients after permanent treatment discontinuation in [Section 1.3.2](#)) and alternate visits during the planned treatment period may be conducted by phone (those with odd visit numbers, except for the planned EOT), as can visits F1 and F2.

Under exceptional circumstances when a patient cannot come to the site for a scheduled visit, a phone contact can be made. During the phone contact, at least information about AEs, concomitant medication and COPD exacerbation events should be collected.

Post IMP treatment follow-up:

Upon completing the 24-52 weeks randomized IMP treatment, patients will continue background therapy and enter the 20-week safety follow-up period.

Number of participants:

Approximately 340 patients will be randomized in this study (170 patients per arm) of which approximately 50% of patients should present with a blood eosinophil count of $\geq 250 /\text{mm}^3$ and about 50% of patients with a blood eosinophil count of $<250 /\text{mm}^3$. All randomized participants who receive at least 1 dose of IMP will be included in the efficacy and safety analysis. See [Section 9.2](#) for sample size determination and [Section 9.3](#) for analysis populations.

Intervention groups and duration:

Study participation for each patient will be up to a total of approximately 46 weeks to 76 weeks, including up to 4 weeks of screening, 24 weeks to 52 weeks of IMP treatment period, and 20 weeks of post IMP treatment period.

Study intervention(s)

Investigational medicinal product(s)

SAR440340

- Formulation: Sterile SAR440340 will be provided in one 20 mL vial containing 287 mg of lyophilisate drug product. One vial of lyophilisate drug product (287 mg) is reconstituted with 2.5 mL of sterile water for injection resulting in 2.9 mL of 100 mg/mL SAR440340. A volume of 1.5 mL per injection will be withdrawn from the vial. Patients will receive 2 injections per dose

- Route(s) of administration: Subcutaneous injection (sites should alternate between the upper thighs, 4 quadrants of the abdomen or the upper arms, so that the same site is not injected twice during consecutive visits)
- Dose regimen: 2 SC injections q2w for 24-52 weeks.

Matching placebo for SAR440340

- Formulation: Sterile placebo will be provided in one 20 mL vial containing lyophilisate placebo. One vial of lyophilisate is reconstituted with 2.5 mL of sterile water for injection resulting in 2.9 mL IMP. A volume of 1.5 mL per injection will be withdrawn from the vial. Patients will receive 2 injections per dose
- Route(s) of administration: Subcutaneous injection (sites should alternate between the upper thighs, 4 quadrants of the abdomen or the upper arms, so that the same site is not injected twice during consecutive visits)
- Dose regimen: 2 SC injections q2w for 24-52 weeks.

Noninvestigational medicinal products(s)

Background therapy

Patients should continue their established standard of care background therapy for COPD throughout the study (double therapy [LABA + LAMA or ICS + LABA or ICS + LAMA] or triple therapy [ICS + LABA + LAMA]).

- Formulation: Dry powder inhaler (DPI), metered dose inhaler (MDI) or pocket nebulizer
- Route(s) of administration: Oral inhalation
- Dose regimen: As prescribed

Patients must be willing to stay on their established background medication for COPD throughout the duration of the study. After successful management of an acute exacerbation of COPD (e.g. with oral corticosteroids and/or antibiotics), all efforts should be made to resume the initial background COPD treatment regimen if in the investigator's opinion this is medically acceptable. After 1 severe or 2 moderate exacerbations of COPD, dose adjustments in background therapy will be permitted for symptom control and as needed for the remainder of the trial period.

Reliever Medication

Patients may use albuterol/salbutamol or levalbuterol/levosalbutamol (including ipratropium or ipratropium/short-acting β agonists [SABA] combinations) as reliever medication as needed during the study. Nebulizer solutions may be used as an alternative delivery method.

- Formulation: Dry powder inhaler (DPI), metered dose inhaler (MDI) or pocket nebulizer
- Route(s) of administration: Oral inhalation

Dose regimen: As prescribed.

Statistical considerations:

- **Primary efficacy analysis:**

For the primary efficacy endpoint the annualized exacerbation rate, a negative binomial regression model will be used to assess treatment differences. The model will include the total number of events occurring during the treatment period (up to Week 52) as response variable, and the treatment group, the baseline eosinophil strata and region (pooled countries) as covariates. Log-transformed observation duration will be the offset variable. Parameters will be estimated using the maximum likelihood method with the Newton-Raphson algorithm.

Comparison of the annualized event rates between the treatment group and the placebo group will be made within this model and the rate ratios and their 95% confidence intervals will be estimated.

In the case of premature discontinuation of study drug, a secondary analysis will include events up to 14 days after the last dose.

Using the same method, subgroup analyses will be performed separately by the baseline eosinophil levels (≥ 250 /mm³ versus < 250 /mm³).

- **Analysis of secondary endpoints:**

Key secondary endpoint

The key secondary efficacy endpoint the average change from baseline to Week 16- 24 in pre-bronchodilator FEV1 will be analyzed using a mixed-effect model with repeated measures (MMRM) approach. Model-based averages across Weeks 16, 20 and 24 will be compared between the treatment groups. The dependent variable is the change from baseline in pre-bronchodilator FEV1 at each time points. The model will include baseline FEV1 value, treatment group, visit, and treatment-by-visit interaction, the baseline eosinophil strata, and region (pooled countries), as covariates. An unstructured correlation matrix will be used to model the within-patient correlations. Parameters will be estimated using restricted maximum likelihood method with the Newton-Raphson algorithm. Additional covariates such as the background medications, age, height, gender, race and smoking status will be considered for inclusion in the analysis model based on evaluation of blinded data and the final analysis model documented in the statistical analysis plan (SAP).

Comparison between the treatment group and the placebo group will be made within this model and the least square mean difference and their 95% confidence intervals will be estimated.

In the case of premature discontinuation of study drug the primary analysis will include data up to 14 days after the last dose.

Subgroup analyses will be performed using the same method by baseline eosinophil levels (≥ 250 /mm³ versus < 250 /mm³).

Other secondary efficacy endpoints:

Change from baseline to Week 24 in FEV1 post-bronchodilator will be analyzed in the same way as the key secondary endpoint.

Similar analytic method will be applied to analyze change from baseline to time points past Week 24 in FEV1 (both pre-bronchodilator and post-bronchodilator).

Time to first moderate or severe AECOPD will be analyzed using a Cox regression model with treatment, baseline eosinophil strata, and region (pooled country) as covariates. The Kaplan-Meier (K-M) method will be used to estimate the probabilities of first AECOPD at specific time points for each group. Additional covariates will be considered based on evaluation of blinded data and the final analysis model documented in the SAP.

- **Safety analysis**

[figure not shown]
Safety analyses will be descriptive, based on the safety population. The safety analysis will focus on the treatment-emergent adverse event (TEAE) period. This period is defined as the time from the first administration of the IMP to 22 weeks after the last administration of the IMP. During the study, unblinded data will be reviewed on an ongoing basis for safety and efficacy by a Data Monitoring Committee (DMC).

Data Monitoring Committee: Yes

An internal DMC will be comprised of individuals with expertise in the diseases under study, biostatistics, or clinical research. The DMC members are independent of the project/study teams and are not involved in the study conduct. The primary responsibilities of the DMC are to review and evaluate the study data during the course of the trial and make appropriate recommendations regarding the conduct of the clinical trial to project/study team.

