β-hCG = Human chorionic gonadotropin-beta; BID = twice daily assessments; CAT = COPD Assessment Test; continuous = subsequent visits during the treatment period; COPD = chronic obstructive pulmonary disease; cont. = continuous; DNA = Deoxyribonucleic acid ; EDTA = Ethylenediaminetetraacetic acid ; EOS = End of Study; EOT = End of treatment; EQ-5D= Euro Quality of Life-5 Dimension questionnaire; EXACT = Exacerbations of COPD tool (EXACT); HIV = human immunodeficiency virus; IgE = Immunoglobulin E; IMP = Investigational Medical Product; IVRS = Interactive Voice Response System; IWRS = Interactive Web Response System; LABA = Long-acting β2 adrenergic agonist; LAMA = Long-acting muscarinic antagonist ;PARC = Pulmonary and activation-regulated chemokine; PK = Pharmacokinetic; RNA = Ribonucleic acid; SABA = Short-acting beta-agonists; SAEs = Serious adverse events; SC = subcutaneous; SGRQ = St. George's Respiratory Questionnaire.

a Randomization/baseline Visit is defined as Day 1. The visit schedule should be adhered to within ±3 days for the screening period and randomized IMP treatment period, and ±5 days for the 2 visits during the post IMP treatment period.

b All assessments at Visit 2 (Day 1) are to be conducted pre-IMP dose with the exception of the assessment of local tolerability of SC injections.

c End-of-treatment visit: See Section 4.1 for patients who discontinue treatment.

d Can be performed with a phone call.

e Chest X-ray to be performed unless a <6 month old chest x-ray/chest CT/chest MRI is available. In case chest-X-ray is not feasible due to local regulations, magnetic resonance imaging (MRI) will be performed.

f The COPD Assessment Test (CAT) is to be registered through the patient's electronic diary.

g IMP (SAR440340 or placebo) to be administered every 2 weeks at the site. Last dose will be given 2 weeks prior to planned EOT visit eg, for patients with 52-week treatment period the last dose will be taken at Week 50, or earlier, as directed by the sponsor. Patients should be monitored by site personnel for at least 30 minutes after administration of all IMP injections. Monitoring period may be extended as per country specific requirements.

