2.1.4 Safety endpoints

The safety analysis will be based on the reported adverse events (AEs) and other safety information, such as clinical laboratory data, vital signs, electrocardiogram (ECG), etc.

Observation period

The observation period will be divided into 4 epochs:

- The **screening** epoch is defined as the time from the signed informed consent date up to the first administration of the IMP.
- The **treatment** epoch is defined as the time from the first administration of the IMP to the last administration of the IMP + 14 days.
- The **residual treatment** epoch is defined as the time from the last administration of the IMP + 15 days to the last administration of the IMP + 154 days.
- If applicable, the **post-treatment** epoch is defined as the time from the last administration of the IMP + 155 days to the patient's end of study (defined as last protocol-planned visit or the resolution/stabilization of all serious adverse events and adverse events with pre-specified monitoring).

The treatment-emergent adverse event (TEAE) period will include both **treatment** and **residual treatment** epochs.

The on-study observation period is defined as the time from the first administration of the IMP to the end of the study.

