2.4.5 Analyses of safety data

The summary of safety results will be presented by treatment group.

General common rules

All safety analyses will be performed on the safety population as defined in [Section 2.3.2](#), unless otherwise specified, using the following common rules:

- Safety data in patients who do not belong to the safety population will be listed separately.
- The baseline value is defined as the last available value prior to the first dose of the IMP.
- The potentially clinically significant abnormality (PCSA) values are defined as abnormal values considered medically important by the Sponsor according to predefined criteria/thresholds based on literature review and defined by the Sponsor for clinical laboratory tests, vital signs, and ECG (PCSA version dated May 2014, see [Appendix A](#)).
- PCSA criteria will determine which patients had at least 1 PCSA during the treatment-emergent adverse event period, taking into account all evaluations performed during the treatment-emergent adverse event period, including nonscheduled or repeated evaluations. The number of all such patients will be the numerator for the on-treatment PCSA percentage.
- The treatment-emergent PCSA denominator by group for a given parameter will be based on the number of patients assessed for that given parameter in the TEAE period by treatment group on the safety population.
- For quantitative safety parameters based on central laboratory/reading measurements, descriptive statistics will be used to summarize results and change from baseline values by visit and treatment group. Summaries will include the endpoint value. The endpoint value

is commonly defined as the value collected at or just prior to the last dose date +14 days, or at the end of treatment visit, whichever comes later. If this value is missing, this endpoint value will be the closest value prior to the last dose intake. The worst value is defined as the nadir and/or the peak post-baseline (up to last administration of IMP) according to the direction (minimum or maximum) of the abnormality as defined in the PCSA list.

- The analysis of the safety variables will be essentially descriptive and no systematic testing is planned.

All safety values including unscheduled measurements will be assigned to the appropriate safety analysis visit window defined in [Section 2.5.4](#).

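### The treatment-emergent period stops on the planned end-of-study day, so a compliant EOS visit after day 154 from the last dose misses the PCSA incidence tables

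*Protocol*

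**What the plan says.** **Length of the period.** The protocol synopsis (1.1, safety analysis) defines it in these words: "This period is defined as the time from the first administration of the IMP to 22 weeks after the last administration of the IMP". SAP 2.1.4 builds it from the treatment epoch plus a residual epoch running from "the last administration of the IMP + 15 days to the last administration of the IMP + 154 days". A post-treatment epoch, outside the TEAE period, covers "the last administration of the IMP + 155 days to the patient's end of study".

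**Position of EOS.** Footnote g to the schedule (protocol 1.3.1) states: "Last dose will be given 2 weeks prior to planned EOT visit". It adds that "for patients with 52-week treatment period the last dose will be taken at Week 50". Safety follow-up is 20 weeks (protocol 4.1). The visit-window tables in SAP 2.5.4 put EOS at target Day 505.

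**Permitted timing.** Footnote a to the schedule allows ±"5 days for the 2 visits during the post IMP treatment period". Protocol 6.1.1 gives the dosing interval as 14 ± 3 days.

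**What is measured at EOS.** SAP 2.1.4.3 to 2.1.4.6 schedule laboratory tests, urinalysis, vital signs, ECG and physical examination at this visit.

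**How results are counted.** SAP 2.4.5 says: "PCSA criteria will determine which patients had at least 1 PCSA during the treatment-emergent adverse event period". The denominator is likewise limited to patients assessed within that period. SAP 2.4.5.3, 2.4.5.4 and 2.4.5.5 repeat the restriction for laboratory, vital-sign and ECG tables. Adverse events are assigned by when they developed, worsened or became serious (SAP 2.1.4.1).

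**The concern.** The cutoff and the planned EOS visit fall on the same day, so there is no slack between them. EOS is the last scheduled safety assessment. Whether its results enter the PCSA incidence tables depends on whether the patient came slightly early or slightly late, although both are within the schedule. An adverse event first detected at a late EOS visit, with onset then, moves to the post-treatment epoch. There it is always listed but summarised only if the number of events is judged large enough (SAP 2.4.5.1).

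The cutoff does not look like a deliberate exclusion of EOS. The 154 days equal the planned dose-to-EOS interval, the post-treatment epoch is described as applying only where applicable, and protocol Table 15 plans cumulative AESI incidence at Week 72, the nominal EOS week. What is at stake is the completeness of the end-of-follow-up safety tables.

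**Working it through.** **1. Reproduce the documents' figure.** Study day = 1 + 7 × week.

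- Last dose, Week 50: 1 + 350 = Day 351.
- EOT, Week 52: 1 + 364 = Day 365, which is last dose + 14.
- EOS, Week 72: 1 + 504 = Day 505, which is EOT + 140.
- End of TEAE period: 351 + 154 = Day 505.

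The same holds at the minimum duration. A 24-week patient has last dose on Day 155, EOT on Day 169 and EOS on Day 309, and 309 − 155 = 154. The documents are consistent with each other, and the slack is zero.

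**2. Apply the permitted windows.** Let *d* be the offset of the last dose from its planned day (−3 to +3) and *e* the offset of EOS (−5 to +5), both in whole days. Then

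days from last dose to EOS = 154 + *e* − *d*,

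and EOS lies outside the TEAE period when *e* > *d*. The range is 154 − 5 − 3 = 146 to 154 + 5 + 3 = 162 days.

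| Last-dose offset *d* | EOS offsets outside the period | Number of 11 |
|---|---|---|
| −3 | −2 to +5 | 8 |
| −2 | −1 to +5 | 7 |
| −1 | 0 to +5 | 6 |
| 0 | +1 to +5 | 5 |
| +1 | +2 to +5 | 4 |
| +2 | +3 to +5 | 3 |
| +3 | +4, +5 | 2 |

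Total: 8 + 7 + 6 + 5 + 4 + 3 + 2 = 35 of 7 × 11 = 77 combinations (45%). With the last dose on its planned day it is 5 of 11, also 45%. If the last dose was 3 days early, an EOS visit exactly on time is already at day 157 and outside. If it was 3 days late, an EOS visit 1 to 3 days late is still inside.

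**3. Trace each kind of result from a visit at day 155 or later.**

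- PCSA incidence: excluded from numerator and denominator.
- Adverse event with onset, worsening or seriousness from day 155: post-treatment.
- Adverse event that began by day 154 but was reported at the late visit: remains a TEAE.
- Missing or partial onset date: remains a TEAE unless the available information shows otherwise (SAP 2.4.5.1 and 2.5.3).
- By-visit summaries: retained, because values are mapped by study day and the last window has no upper limit (≥435 for laboratory and ECG, ≥463 for vital signs).
- Listings: retained, with PCSA flags.
- Liver display by duration of exposure: retained, because it uses any post-baseline visit (SAP 2.4.5.3).

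**4. Share of the schedule concerned.** By the SAP visit lists, EOS is one of six post-baseline laboratory sets for a 52-week patient (Visits 6, 10, 14, 20, EOT, EOS) and one of four for a 24-week patient. Vital signs are taken at all visits, so EOS is a far smaller part of those data.

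**5. Check the remedy.** The largest permitted interval is 162 days, so a cutoff at last dose + 162 contains all 77 combinations.

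**The case against.** The best defence is that a fixed interval after the last dose is a legitimate analysis choice, stated consistently. Protocol and SAP agree on it, the SAP gives the post-treatment epoch its own reporting, and the same limit governs concomitant medications (SAP 2.1.2). A patient counts once for a PCSA, so only someone whose first qualifying abnormality appears at a late EOS visit is affected. The safety analysis is descriptive. SAEs within AESI categories are counted regardless of treatment-emergent status, and on-study deaths are counted to the end of study. All of this stands and limits the weight of the point. It does not explain why a scheduled, compliant safety assessment should be in or out of the PCSA tables by a day or two.

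Three stronger readings are tempting and are not supported.

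- **Everything reported at a late EOS visit leaves the TEAE tables.** It does not. Classification follows onset, worsening or seriousness, not the date of the visit.
- **About 45% of completers are affected.** With 20% drop-out, 340 × 0.80 = 272 completers, and 272 × 35/77 is about 124. The documents give no distribution of visit timing, so this only reweights calendar combinations. It also says nothing about how many patients have a new abnormality at EOS.
- **The by-visit and PCSA tables contradict each other.** They are different displays and need not agree, though they will rest on different EOS data.

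One premise is also less than certain. The window text names two post-treatment visits, while the schedule has three (F1, F2 and EOS). EOS is probably covered, since F2 may be a telephone call, but the text does not say so.

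**Conclusion.** The point holds in limited form. The TEAE period ends on the planned EOS day, and a compliant EOS visit at 155 to 162 days after the last dose is excluded from the PCSA incidence tables. Neither document corrects this. The effect is a modest under-count of abnormalities first seen at EOS. The rule is the same in both arms, so no directional bias is shown, and the values remain in by-visit summaries and listings. The number of patients affected cannot be estimated from the documents.

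This rests on three assumptions: the ±5-day window applies to EOS; last dose and EOS are each scheduled from their planned study days; and the patient completed planned treatment. If sites scheduled EOS from the actual last dose instead, the range would be 149 to 159 days and 5 of 11 permitted days would still fall outside. Patients who stop early but keep to the original schedule can have EOS well beyond 154 days for a different reason. This is a cheap improvement and not a threat to the trial's conclusions.

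**What to change.** Before database lock, in the protocol synopsis and SAP 2.1.4:

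- End the residual treatment epoch and the TEAE period at last dose + 162 days (154 + 5 + 3) for all patients.
- Start the post-treatment epoch at last dose + 163 days.
- In SAP 2.1.2, move the concomitant-medication cutoff to + 162 days and the post-treatment medication start to + 163 days.
- Reconcile the visit-window text in protocol 1.3.1 and 4.1, which names two post-treatment visits, with the schedule, which has three, so that EOS is clearly covered.

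A single cutoff is better than ending the period at each completer's EOS date. That alternative would make the period depend on when the patient attended and would give completers and early discontinuers different definitions.

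The cost is a few lines of text and matching changes to the analysis programs. The downside is up to 8 extra days of background events per patient in both arms. The on-treatment death category, which uses the same period, would lengthen with it. EOS visits outside the permitted window could still fall after the cutoff, as they can now.
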